6.1. Informed Consent

Part 1:

Informed consent will be sought from the parent/guardian of the patient before any study specific procedures are performed according to standard Good Clinical Practice regulations. Written participant information and informed consent in the local language will be presented to the parent/guardian of the participants detailing no less than: the exact nature of the study; the implications and constraints of the protocol; the known side effects and any risks involved in taking part. It will be clearly stated that participation is voluntary and that the participant or their parent/guardian is free to withdraw consent for participation from the study at any time for any reason without prejudice to future care, and with no obligation to give the reason for withdrawal.

The parent/guardian will be allowed as much time as possible to consider the information and take the opportunity to question the Investigator, or other independent parties to decide whether they will (or allow his/her child to) participate in the study. However, the study team will try to ensure that no more than one hour elapses between presentation and treatment either on or off the study.

Written informed consent will then be obtained by means of the parent/guardian's dated signature and dated signature of the person who presented and obtained the informed consent. If the parent/guardian is illiterate and unable to read and write, a witness is required to be present during the entire informed consent process. The parent/guardian provides his/her thumbprint, and the witness provides his/her signature and date on the consent form. A copy of the signed informed consent document(s) will be given to the parent/guardian of the patient.

Assent is not required for either of the countries where the study will recruit.

Part 2:

A total of three various types of written informed consents will be used.

The first written informed consent will be used to study staff and health staff. Both SSIs and survey will be conducted among study staff and health staff.

The second informed consent for video record will be conducted among study staff to record the procedure of preparing the 1-step versus 2-step artesunate injections and administering it to patients. This video will be used to familiarize the policymakers before conducting the SSIs with them.

The third written informed consent will be collected from policymakers and stakeholder who will be interviewed using SSI-guide.

Part 3:

No specific consent process is required for this sub-study.

6.2. Screening, Eligibility and Baseline Assessments

Part 1:

Patients who present at the participating sites will be screened to assess eligibility. Full consent will be obtained before any enrolment procedures are conducted. A screening log will be kept.

6.2.1. Screening tests

These will be EDTA-anticoagulated blood or a finger prick for:

- Malaria RDT

If no signs of severe diseases and RDT-positive, then where microscopy is available promptly:

- A parasite count from Giemsa or Field stained thick and thin blood films
- Haematocrit

6.2.2. Demographics and Medical History

Basic demographic data (e.g., sex, age, address, prior treatment and previous participation in this or previous studies), and a full medical history will be recorded by the study staff. To reduce the waiting time to drug administration, all information that are not immediately relevant for the inclusion and clinical care of the patient (such as epidemiological data regarding malaria risk factors) might be collected after the patient is stabilised and parents/caregivers feel comfortable.

6.2.3. Physical Examination and Vital Signs

Physical examination will be conducted by a qualified study team member. Weight, height, pulse rate, blood pressure, respiratory rate, temperature, and spleen and liver size will be recorded if palpable. Non-invasive neurological exams will be performed to monitor recovery and neurological sequelae. This will be done before discharge from the study ward, on day 28 of follow up. And, for participants who have sequelae at day 28, neurological exams will be done at month 3, month 6, and month 12.

6.2.4. Drug history

All prescribed or over-the-counter and traditional medications used within the last 7 days will be recorded. Any drug allergies will be recorded.

6.3. Randomisation and blinding

Patients will be randomised to treatment with either conventional 2-step parenteral artesunate (1) or 1-step parenteral artesunate (2). Patients who fulfil all the inclusion criteria and have none of the exclusion criteria will be randomised 1:1 to one of the two treatment arms according to a randomisation schedule. Randomisation will be in blocks of 8-12. Allocation will be done by drawing the next sequential numbered opaque envelope, which contains the study number and treatment allocation.

The patients will be assigned a study arm through a computer-generated randomisation schedule by the study statistician in MORU. Individual, sealed and sequentially numbered envelopes will be provided for each trial site with one envelope per patient, indicating the treatment allocation. This is an open-label study so the blinding of investigators and patients is not applicable. However, the randomisation procedure allows for adequate drug allocation concealment before envelopes are

opened. All laboratory investigations will be performed without knowledge of the treatment allocation.

6.4. Procedures during hospitalisation

A physical examination will be performed daily and every six hours on indication. Vital signs recorded hourly for unstable patients, then 6 hourly for stabilised patients, and at each FU visit. A symptom questionnaire will be taken daily to help identify adverse events. All studies procedure will follow appendix 3.

6.5. Follow-up visits

Patients will be asked to come back for a follow-up visit at day 7, 14, 21 and 28. Patients will not be followed up longer. In case of unresolved important sequelae at day 28, the patient will be followed and treated longer in order to provide the appropriate clinical care. All follow up studies procedure will follow appendix 3.

Additional unscheduled visits

Patients presenting to the clinic with a fever or other symptoms on unscheduled days will be assessed by the study physician. Their temperature will be recorded and blood smear will be made for any patient with a documented fever (tympanic temperature $\geq 37.5^{\circ}\text{C}$) or a history of fever. Patients will be treated as clinically indicated.

The monitoring of the patients is not strictly defined in the protocol and should be done according to good medical practice. An exception is monitoring of blood glucose. Blood glucose will be measured on admission and between 4 and 6 hourly thereafter for at least 24 hours or until the patient recovers consciousness and can eat if longer than 24hrs. Blood glucose can be checked at any other time as clinically indicated. The parameters that will be monitored during admission will vary slightly between the study sites, according to different requirements expressed by the IRBs of the different countries. If a patient's clinical situation deteriorates the doctor on call has to be informed immediately. Appropriate steps for the treatment of (complications of) severe malaria are outlined appendix 4.

Time window for follow up visits

The time-window for the visit on Day 7, 14, 21 is +/-3 days and for the visits on Days 28 is -3/+7 days

6.6. Blood sampling

6.6.1. On admission (time 0)

Patients will have an intravenous catheter inserted for at least the first 24 hours. An SOP will be provided instructing how this is to be done and how to take blood for protocol tests.

On study admission, immediately before drug administration, blood will be collected according to appendix 3 for the following:

- Parasite count (thick and thin films) and Hct.
- Haemoglobin
- Full blood count
- Reticulocyte count (EDTA-anticoagulated)
- Biochemistry assessments including bilirubin, ALT, AST, Alkaline Phosphatase, and creatinine levels, LDH and any other tests that might be deemed relevant by the treating physician.

Blood glucose In this study patients will be enrolled based on clinical signs of severity and the results of the Rapid Diagnostic Test for reasons of administering the treatment for severe malaria as soon as possible, as the microscopy results are not available before 1 hour. In the case the slides from screening and admission are negative the treating physician will review the diagnosis and change the patient management accordingly. The patient will however be retained in the study (intention to treat).

6.6.2. During hospitalisation

During hospitalisation, patients will have blood taken for malaria films and haematocrit at 4h, 8h and 12h and thereafter every 6 hours until parasite clearance (when two consecutive malaria slides are negative). Haematocrits will be done whenever a malaria blood film is made.

During hospitalisation (24 hr, 48 hr 72 hr and 96 hr and follow-up visits (day 7, 14, 21, 28), blood will also be taken for:

- 1 mL EDTA: Full blood count, , and Hb
- Reticulocyte count
- 1 mL heparinised blood: biochemistry assessments including bilirubin, ALT, AST, Alkaline Phosphatase, and creatinine levels, and LDH.

Other tests that might be deemed relevant by the treating physician for the care of the patients can be performed.

Note: Once parasitemia has been cleared and the patient tolerates oral antimalarial medications. The patients can be discharged according to the judgement of treating physician.

6.6.3. Blood volumes

The blood volumes for the protocol mandated tests are detailed in the study schedule. Maximum blood volumes are presented below for children. The maximum blood volume will be approximately **14 ml**. For children of 5 kg and more, this is less than 4% of the total blood volume during the whole study period and well below the 10% of total blood volume taken over 8 weeks as recommended by WHO *Bulletin of the World Health Organization 2011:89:46-53* (On average the total blood volume is 80 ml/kg body weight)].

Test	n. test	mL blood for one sample	N.	Total	Time points
RDT	1	0.02	1	0.02	Admission
Malaria film	1	0.06	25	1.5	Admission and H0,4,8,12, then +6 hourly until H48, then 12 hourly until 2 consecutive negative slides, day 7, 14, 21, 28 and unscheduled (n) (max expected 25 blood slides)
Biochemistry tests (ALT, AST, BIL, AKP, Cr, LDH)	5	1	9	9	H0, 24, 48, 72 then day 7, 14, 21, 28, n
Haemoglobin	1	0.08	9	0.72	H0, 24, 48, 72 then day 7, 14, 21, 28, n
Haematocrit	1	0.05	25	1.25	Same time points as slides
Full Blood Count	1	0.1	9	0.9	H0, 24, 48, 72 Days,7,14,21,28,n
Reticulocytes	1	0.05	9	0.45	H0, 24, 48, 72 Days,7,14,21,28,n
Total				13.84	

Part 2:

A mixed method social science study that entails SSIs and survey with study staff, health workers and policymakers and stakeholders, to assess the acceptability, feasibility, pros and cons, costs, and logistics and training implications of 1-step AS vs 2-step conventional AS. Each interview will take around 30 - 45 minutes. The interview will be audio-recorded, if participant allowed. Topic guide will be used during the interview.

For survey/questionnaire, a maximum number of relevant participants (150 study staffs and health care staffs) will be attempted to be recruited from two sites.

Part 3:

1. Gather all necessary data from multiple sources.
2. Summarize relevant findings related to real-life practice from Part 1 & Part 2 of study.
3. Calculate cost types: consumables, training, time savings, shipping, wastage, storage.
4. Calculate costs: fixed, one-time, variable costs
5. Calculate unit costs
6. Compare costs and over period of time under different scenarios
7. Rank best options over selected time periods
8. Assessment of uncertainties and externalities

The costing analysis will occur during the second half of the trial as data from Part 1 and Part 2 become available.

A cost analysis of 1-step parenteral AS using data from Part 1 & Part 2. This will assess health facility-level costs, and health system costs to encompass all costs of a potential change from conventional to 1-step artesunate, including re-training, materials, drug replacement. Unit costs will be assigned to healthcare worker time spent on managing patients with severe malaria (derived from the time and motion surveys). Micro costing will be carried out in each of the sites to estimate the costs of equipment and consumables associated with provision of artesunate with each of the formulations. The resulting labour and consumable mean costs will be compared in patients treated with 1-step vs conventional artesunate formulation.

In addition to time measurement, the observer will also record the resources used for the administration of artesunate. This will include the vials themselves, as well as other consumables required for the administration (syringes, needles, catheters, etc.).

Unit costs for these resources will be obtained online and this does not require data collection on site. Costs can be obtained by communication with representatives of companies, hospital administrators and malaria control programme officers. This will be sufficient to capture the specific costs for the administration of the treatments, and assumes that other care and length of stay will not be affected (consistent with the working assumption that there will be no difference in clinical outcomes).

6.7. Study drug regimens

Overview of drug regimens	
1-step AS-arm	2-step AS-arm

1-step parenteral AS
 
New injectable artesunate (Argesun) 60mg
 
Each vial of powder contains 60mg artesunate. Each ampoule of 6 ml solvent contains: sodium bicarbonate 8.4mg/ml; arginine 20mg/ml.
 
Guilin Pharma, Guangxi, China Artesunate 2.4 mg/kg STAT on admission, 12hrs, then daily. <20 kg children will get artesunate 3.0 mg/kg. Minimal 3 doses.
 
FOLLOWED BY
 
Oral artemisinin combination therapy x 3 days
	
Conventional 2-step parenteral AS
 
Conventional injectable artesunate (Artesun) 60mg
 
Each vial of powder contains 60 mg artesunate. Each ampoule of 1 ml solvent contains 50 mg sodium bicarbonate. Each ampoule of 5 ml diluent contains 45 mg sodium chloride.
 
Guilin Pharma, Guangxi, China Artesunate 2.4 mg/kg STAT on admission, 12hrs, then daily. <20 kg children will get artesunate 3.0 mg/kg. Minimal 3 doses.
 
FOLLOWED BY
 
Oral artemisinin combination therapy x 3 days

Patients will be treated with weight-based doses according to the schedule in Appendix 1.

The ACT used will be artemether-lumefantrine if available, given according to manufacturer's instructions. The ACT will be administered by study medical or nursing staff while the patients are hospitalised. Directly Observed Therapy (DOT) will be done if possible, but in all cases the first dose of ACT will be by DOT. During DOT, if the patient vomits within half an hour after intake of ACT, the full dose will be repeated. If vomiting occurs between half and one hour, half of the dose will be repeated. If vomiting occurs more than one hour after drug administration, no repeat dosing will be done. Repeat doses will be recorded on the CRF. If vomiting within 1 hour occurs more than one time, no repeat dosing is allowed. The patient will be treated at the discretion of the investigator.

6.8. Discontinuation/ Withdrawal of Participants from the Study

Each participant (or the responsible caregiver) has the right to discontinue the study drug or the study participation at any time without giving a reason.

The investigators may as well decide to discontinue participation in the study of a participant if necessary.

The reason for withdrawal or discontinuation, if available, will be recorded in the CRF. If the study drug or participation in the study is discontinued due to an adverse event, the investigator will arrange for follow-up visits at least until the adverse event has resolved or stabilised.

6.9. Source Data

Part 1 and 2

Source documents are original documents, data, and records from which participants' CRF data are obtained. These include, but are not limited to, hospital records (from which medical history and previous and concurrent medication may be summarised into the CRF), clinical and office charts, laboratory and pharmacy records, diaries, microfiches, radiographs, and CRFs.

CRF entries will be considered source data if the CRF is the site of the original recording (e.g., there is no other written or electronic record of data). In this study, the CRF will be used as the source document for most of the data points.

All documents including audio-records, survey questionnaire forms will be stored safely in confidential conditions. On all study-specific documents, other than the signed consent form, the participant will be referred to by the participant number, not by name.

6.10. Definition of end of the trial

The end of the trial will be the date of the last visit of the last participant.

7. STUDY DRUGS

7.1 Storage of Study Drugs

All efforts will be made to store the study drugs in accordance with the manufacturers' recommendations in a secure area.

7.2 Compliance with Study Drugs

Parenteral study drugs will be administered by study medical staff (either a doctor or nurse). The first dose of ACT will be administered by DOTs and if the patient vomits ACT, and is re-dosed; this will be recorded in the CRF. If vomiting within 1 hour occurs again after retreatment, no repeat dosing is allowed. In this case the patient will be treated at the discretion of the Investigator. The patient may be discharged if recovered in the opinion of the study physician even if the full 3-day course of ACT is not complete. All drug doses will be recorded in the CRF.

7.3 Accountability of the Study Treatment

All movements of study medication will be recorded. Both study medication of individual patient and overall drug accountability records will be kept up to date by the study staff.

7.4 Concomitant Medication

Throughout the study, investigators may prescribe concomitant medications or treatments deemed necessary. Any medication, other than the study medication taken during the study will be recorded in the CRF.

8. SAFETY REPORTING

This trial will use parenteral artesunate followed by an ACT (expected to be artemether-lumefantrine, or other ACT), drugs that are registered and have been evaluated extensively.

To allow for comparison of safety and tolerability of 1-step injectable artesunate compared to conventional injectable artesunate we will record and review all Adverse Events (AEs) and Serious Adverse Events, (SAEs) that occur in the study.

A symptom questionnaire will be performed daily during hospitalization and at each subsequent visit to the health care facility, to aid in the identification of adverse events.

The investigator is responsible for the detection and documentation of events meeting the criteria and definition of an adverse event (AE), or serious adverse event (SAE), as provided in this protocol.

All SAEs, and AEs will be promptly documented from the moment of randomization in the study to discontinuation of the patient from study participation. Any events occurring between screening and randomization will be considered as baseline, pre-existing conditions. Any conditions that were present at baseline will not be considered adverse events unless the grade of the condition deteriorates.

Each adverse event will be graded according Common Terminology Criteria for Adverse Events (CTCAE) version 5.0:

https://ctep.cancer.gov/protocolDevelopment/electronic_applications/ctc.htm#ctc_50

All adverse events must be recorded in the AE /SAE CRF. To avoid colloquial expressions, the adverse event should be reported in standard medical terminology. Whenever possible, the adverse event should be evaluated and reported as a diagnosis rather than as individual signs or symptoms. If a definitive diagnosis is not possible, then the individual symptoms and signs should be recorded. Whenever possible, the aetiology of the abnormal findings will be documented on the CRF. Any additional relevant laboratory results obtained by the Investigator during the course of this study will be recorded on the CRF.

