8.1 Definitions

8.1.1. Adverse Event (AE)

An AE is any undesirable event or clinical deterioration that occurs to a study participant during the course of the study; that is, from the time of administration of study drugs until study ends (i.e., until the follow up visit) whether or not that event is considered related to the study drugs, or to a concomitant drug or procedure, e.g.

- any unfavourable and unintended symptom
- physical sign
- abnormal laboratory result
- an illness
- any pre-existing condition that has worsened in grade

Any new clinical sign or clinical deterioration that occurs between signing the consent form and the administration of study drugs is not an AE. This information will be recorded in the medical records, as a pre-existing condition.

Condition associated with severe malaria

Common conditions resulting from a deterioration of severe malaria as per list should not be considered or reported as Adverse Events. They are recorded in the specific section of the CRF.

A list of the most common conditions in severe malaria includes,

- Deterioration of BCS or GCS
- Coma not present at admission
- Convulsions not present at admission
- Posturing not present at admission
- Decompensated shock (children systolic BP <70 mm Hg)
- Compensated shock (capillary refill >3sec /temperature gradient)
- Respiratory distress
- Hypoglycaemia (glucose <3 mmol/L)
- Severe anaemia
- Severe bleeding (requiring blood transfusion)
- Hemoglobinuria
- Severe jaundice
- Renal failure (urine output <0.5 mL/kg/hr >24 hours)

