12.4.1. Risks of parenteral artesunate

One of the concerns about the artemisinin derivatives is neurotoxicity, in particular involving the brain stem²⁴. Nevertheless, a discrepancy seems to prevail with regard to the toxicity and safety of the artemisinin family of antimalarials. While these compounds have been found to be virtually void of any serious side effects in humans, their neurotoxicity in animal models has raised concerns about their use^{25,26}. The prolonged presence of artemisinins upon slow release from oil-based intramuscular formulations at several orders of magnitude above the therapeutic level appear to be the main cause of the observed toxicity in laboratory animals.

Artesunate is rapidly and extensively converted to dihydroartemisinin (DHA), the active metabolite, primarily by plasma and erythrocyte esterases. DHA elimination from the blood compartment is also rapid (half-life approximately 45 min). The potential for drug-drug interactions with other medicinal products is limited. *In vitro* drug-interaction studies have demonstrated minimal effects of artesunate on cytochrome P450 isoenzymes. In the limited number of clinical drug-drug interaction studies that have been performed, however, no clinically significant drug-drug interactions have been identified.

Delayed haemolytic anaemia following treatment with injectable artesunate has been observed in children in malaria endemic areas and in non-immune travellers presenting with severe falciparum malaria.²⁷ The risk was most pronounced in patients with hyper-parasitaemia and in younger children. Some cases have been severe and required blood transfusion. The risk of post-artesunate delayed haemolytic anaemia has been reported however to be very low in children in highly endemic settings (Mozambique and DRC) and statistically not different from intravenous quinine¹⁸. Vigilance for delayed onset anaemia is therefore advised, particularly in hyper-parasitaemic patients and younger children, and prolonged follow-up should be considered (e.g. 14-28 days). As the overall benefit-risk ratio remains highly favourable for injectable artesunate in the treatment of severe malaria, WHO strongly recommends its continued use.

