Hypotension is not a common feature of severe malaria and in case of circulatory shock, concurrent septicaemia should be considered. Blood cultures should be taken and the patient should be treated empirically with antibiotics, covering gram-negative bacteria (e.g., the combination of cefotaxime and gentamicin). In case of hypotension, the patient should receive fluid resuscitation. Systemic salmonella infection may develop, presumably because of increased translocation of bacteria in the gut (Mabey 1987). If the patient has been admitted for several days in the ICU, hospital acquired infections should also be considered. Secondary pneumonia is common.

Acidosis in severe malaria can be due to acute renal failure, but usually is a lactic acidosis resulting from tissue hypoxia, generally in the absence of hypotension. Treatment should therefore be directed to optimize the microcirculation, but we have only limited tools to achieve this. Prompt treatment of the parasite causing sequestration and obstruction in small vessels, optimal fluid management and treatment of severe anaemia can all contribute. Using iSTAT results can help in the management of acidosis. If the arterial pH drops below 7.2, 100 ml 8.4% HCO₃ over 30 minutes can be given.

Anaemia is a frequent feature, especially in young children with severe malaria. Transfusion of packed red cells can be restricted to those with haematocrit falling below 20%. It is essential that blood products are negative for transmissible diseases like HIV, hepatitis B, hepatitis C and syphilis.

Disseminated Intravascular Coagulation (DIC)

For those rare patients who develop DIC with bleeding, fresh frozen plasma can be given. In addition, vitamin K should be administered, in a daily dose of 10 mg slowly i.v., for 3 days.

Coma

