Direct bilirubin	X/XX (X.X)	X/XX (X.X)	X/XX (X.X)	X/XX (X.X)	X.XXX
Alanyl transfarase (ALT)	X/XX (X.X)	X/XX (X.X)	X/XX (X.X)	X/XX (X.X)	X.XXX
Aspartate transfarase (AST)	X/XX (X.X)	X/XX (X.X)	X/XX (X.X)	X/XX (X.X)	X.XXX
Alkaline phosphatase	X/XX (X.X)	X/XX (X.X)	X/XX (X.X)	X/XX (X.X)	X.XXX
Hematocrit decrease	X/XX (X.X)	X/XX (X.X)	X/XX (X.X)	X/XX (X.X)	X.XXX

Adverse event grading: grade1 to grade 5 (CTCAE)

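### The SAP plans no time-separated comparison of late anaemia: the acute malarial fall and any delayed post-artesunate fall share one 28-day count judged against the admission grade.

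*Protocol*

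**What the plan says.** **Risk and sampling.** Protocol 12.4.1 describes delayed haemolytic anaemia after injectable artesunate, some of it severe enough for transfusion. It states: "Vigilance for delayed onset anaemia is therefore advised, particularly in hyper-parasitaemic patients and younger children". The same paragraph says the reported risk is very low in children in highly endemic settings. Protocol 6.6.2 schedules the tests: "During hospitalisation (24 hr, 48 hr 72 hr and 96 hr and follow-up visits (day 7, 14, 21, 28), blood will also be taken for" full blood count, Hb, reticulocytes and biochemistry including LDH. Haematocrit is taken at the same follow-up visits (6.6.3 and Appendix 3).

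**Adverse event rules.** Section 8 says "Any conditions that were present at baseline will not be considered adverse events unless the grade of the condition deteriorates". Section 8.1.1 counts "any pre-existing condition that has worsened in grade". It then adds: "Common conditions resulting from a deterioration of severe malaria as per list should not be considered or reported as Adverse Events". The list that follows includes "Severe anaemia" and haemoglobinuria, and it gives no day after which the exclusion stops. SAP 3.5 limits its summaries to events that are new or more intense after study drug.

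**Analysis.** The endpoint is the incidence of adverse events over the first 28 days (protocol 5.4.3, SAP 2.1.3). SAP Table 5 presents this by arm as n/N in two grade bands. Three rows bear directly on anaemia or haemolysis: "Hematocrit decrease", haemoglobinuria, and a composite that includes haematocrit below 15% or Hb below 5.0 g/dL. The SAP does not name LDH or reticulocytes. Protocol 9.2.3 provides in general terms for comparing laboratory parameters between arms.

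**The concern.** The documents describe two processes with different timing. One is the anaemia of the disease, of which Appendix 4 says "Anaemia is a frequent feature, especially in young children with severe malaria". The other is a delayed drug effect that follow-up is meant to catch. Young children are among those in whom the protocol says the delayed risk was most pronounced, so the two processes fall in the same patients. A count that starts at admission, uses the admission grade as reference and closes on day 28 mixes them.

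At stake is exploratory objective 4. The new formulation has not yet been used in severe malaria (protocol 3.2), and section 8 says events are recorded so that the two formulations can be compared for safety. For the one delayed haematological effect the protocol singles out, the tables may show mainly malarial anaemia in both arms, although the data to do better will have been collected.

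**Working it through.** The plan gives no figure for anaemia or haemolysis. Its sample size concerns preparation time and is not in question here. The check is mainly a comparison of the rules.

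**1. Three courses under the stated rules**

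- *Child A* worsens in grade on day 1, recovers, and falls again on day 14 to the same or a lesser grade. Table 5 reports patients (n/N), so A is counted once, on day 1. The day-14 fall changes nothing.
- *Child B* is anaemic on admission, recovers or is transfused by the day-7 visit, and falls back to the admission grade on day 14. Against admission the grade has not deteriorated. Read literally, sections 8 and 8.1.1 do not require an adverse event. No text says that recovery resets the reference.
- *Child C* develops severe anaemia on day 14. If the investigator attributes it to deterioration of severe malaria, 8.1.1 keeps it out of adverse event reporting, whatever the day. If it is attributed to the drug, it is reportable. The trial is open-label and the protocol gives no guidance on this attribution for late falls.

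**2. Protocol 8.1.1 against SAP Table 5**

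Section 8.1.1 sends listed conditions that result from deterioration of severe malaria to a separate part of the CRF. Table 5 tabulates similar conditions (haemoglobinuria, severe pallor or very low Hb, shock, respiratory distress) as adverse events. The documents do not say which records feed those rows.

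**3. How one ever/never count dilutes a late difference**

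Let e be the proportion with an early fall in both arms, and d1 and d2 the late-fall proportions, with early and late falls independent. The 28-day proportion in an arm is 1 − (1 − e)(1 − d), so the difference between arms is

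(1 − e) × (d1 − d2).

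The documents give none of these rates. The values below are assumptions chosen to show the mechanism.

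| Assumed e | Share of late difference kept | 20% vs 5% late (15 points) | 10% vs 2% late (8 points) |
|---|---|---|---|
| 30% | 0.7 | 10.5 points | 5.6 points |
| 50% | 0.5 | 7.5 points | 4.0 points |
| 70% | 0.3 | 4.5 points | 2.4 points |

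For e = 50%: 1 − 0.5 × 0.80 = 0.600 and 1 − 0.5 × 0.95 = 0.525, a difference of 0.075. The factor (1 − e) does not depend on the late rates chosen. The differences in points do.

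**4. Visit windows**

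Protocol 6.5 allows ±3 days at days 7, 14 and 21, and −3/+7 at day 28. The day-7 visit can fall on days 4 to 10, the day-14 visit on days 11 to 17, and the day-28 visit on days 25 to 35. The interval between the day-7 and day-14 visits can therefore be 1 day (10 to 11) or 13 days (4 to 17). Any split must use actual sampling dates.

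**The case against.** The best case for the plan has five parts.

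- **Late anaemia is not ignored.** A reader might infer that it is never compared between arms, or that post-baseline Hb is missing from the SAP. Neither is so. Table 5 has the composite with Hb below 5.0 g/dL, haemoglobinuria, bilirubin and haematocrit, all with p-values, and late values can feed those rows. Protocol 9.2.3 permits comparison of laboratory parameters, which can include LDH and reticulocytes. What is missing is a pre-specified comparison separated in time.
- **The event rules can be read more generously.** A relapse after recovery can count as newly started under SAP 3.5, and section 8 prefers a diagnosis to isolated signs. The list in 8.1.1 covers deterioration of malaria, not a drug effect. This stands: child B may be recorded. But it depends on each investigator's reading, so it is wrong to say that such children certainly drop out.
- **The risk may be small.** Section 12.4.1 calls it very low in highly endemic settings, citing DRC, the country of one site, and statistically no different from intravenous quinine. Both arms contain the same active drug.
- **No loss of power can be claimed.** A reader might turn the dilution table into power figures. The documents support no late rates and no difference between arms, so such figures would describe only the assumptions.
- **Safety is exploratory and unpowered** (protocol 3.2 and 9.2.4). This limits the importance of the point. It does not remove the value of an estimate with a confidence interval from data already collected.

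**Conclusion.** The point holds as a gap in definition and analysis, not in sampling. The anaemia-related rows of Table 5 pool the acute and delayed phases. The reference grade is the one at admission. The exclusion list in 8.1.1 has no cut-off day and does not fit the rows of Table 5. No pre-specified analysis isolates a fall after the day-7 visit.

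The conclusion assumes that n/N in Table 5 counts each child once, which its layout indicates, and that no rule outside these two documents resets the reference after recovery. The size cannot be stated from the documents. The structural statement is that a single ever/never count keeps only the fraction (1 − e) of any late difference, given independence and equal early rates. The primary endpoints and the sample size are not affected. This is an inexpensive improvement to exploratory safety reporting.

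**What to change.** 1. **SAP Table 5.** Report the haematocrit row twice: before the day-7 visit, and from the day-7 visit to the day-28 visit. Assign samples by actual date.
2. **SAP 3.5.** Add one exploratory comparison between arms: the change in Hb from the day-7 visit to the lowest value at the day-14, 21 and 28 visits, as a difference with 95% CI. Flag transfused children, give the number of later visits contributing in each arm (a minimum depends on how many values are available), and summarise LDH and reticulocytes alongside.
3. **Protocol section 8.** State that a new fall after documented recovery is recorded as a new event, and define documented recovery, including how a rise after transfusion is treated. Reconcile sections 8 and 8.1.1 with Table 5, saying which CRF records feed the rows for conditions on the 8.1.1 list.

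A blanket second baseline at day 7 for all adverse events is not recommended. With the ±3-day window that reference could lie anywhere from day 4 to day 10, and it would conflict with 8.1.1 and with the definition in SAP 3.5.

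The cost is a few SAP rows and a short addition to section 8. All samples are already scheduled. The downside is that somewhat more anaemia events will be recorded.
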